The Feasibility of the VOICES Digital Health Tool for Elder Mistreatment Screening in the Primary Care Setting

(VOICES-PC Feasibility)

Protocol Number

2000031059

Protocol Version

01/20/2022

Version #1.01

PRINCIPAL INVESTIGATOR:

*[name]
Yale School of Medicine
Department of Emergency Medicine
[name]
[contact]*

Confidentiality Statement:

REVISION HISTORY:

Revision #	Version Date

Synopsis

Primary Objective

The primary objective of this study is to perform a feasibility evaluation of the VOICES screening tool (HIC#: 2000023799) among 80 older adults in primary care settings.

Secondary Objective (if applicable)**Study Duration**

Approximately 10 months.

Study Design

This is a feasibility study of a tablet-based screening tool to identify suspicion of elder mistreatment.

Number of Study Sites

1: Yale Internal Medicine Associates (YIMA).

Study Population

Older adults (age 60+) seen at YIMA.

Number of Participants

80

Primary Outcome Variables

Feasibility and Acceptability

Secondary and Exploratory Outcome Variables (if applicable)

N/A

Abbreviations

Abbreviation	Explanation
EM	Elder Mistreatment
YIMA	Yale Internal Medicine Associates
PSE	Connecticut Protective Services for the Elderly
RA	Research assistant
PC	Primary Care

Glossary of Terms

Glossary	Explanation
----------	-------------

Table of Contents

Preface.....	2
Synopsis	4
Primary Objective	4
Secondary Objective (if applicable).....	4
Study Duration.....	4
Study Design	4
Number of Study Sites	4
Study Population	5
Number of Participants.....	5
Primary Outcome Variables	5
Secondary and Exploratory Outcome Variables (if applicable).....	5
Abbreviations	6
Glossary of Terms.....	7
1 Introduction	11
1.1 Introductory Statement	11
2 Background.....	12
2.1.1 Device Preclinical Experience	12
2.1.2 Device Clinical Experience	12
2.2 Background/prevalence of research topic	12
3 Rationale/Significance	13
3.1 Problem Statement.....	13
3.2 Purpose of Study/Potential Impact	13
3.2.1 Potential Risks.....	13
3.2.2 Potential Benefits	13
4 Study Objectives.....	14
4.1 Hypothesis	14
4.2 Primary Objective	14
4.3 Secondary Objectives (if applicable)	14
5 Study Design	15
5.1 General Design Description.....	15

5.1.1	Study Date Range and Duration	15
5.1.2	Number of Study Sites	15
5.2	Outcome Variables	15
5.2.1	Primary Outcome Variables	15
5.2.2	Secondary and Exploratory Outcome Variables (if applicable)	15
5.3	Study Population	15
5.3.1	Number of Participants	16

1.1 Introductory Statement

This document is a protocol for a human research study. The purpose of this protocol is to ensure that this study is to be conducted according to ICH GCP guidelines, and according to CFR 21 Part 812, other applicable government regulations, and Institutional research policies and procedures.

2 Background

2.1.1 Device Preclinical Experience

The VOICES tool has been developed and tested with more than 800 patients at Yale Emergency Department (IRB Protocol ID:2000023799 and Submission ID:CR00008317).

2.1.2 Device Clinical Experience

In a prior clinical study at Yale Emergency Department (IRB Protocol ID:2000023799 and Submission ID:CR00008317), we developed an innovative digital health tool that runs on tablets called **VOICES** that screens, educates, and motivates older adults to make an informed decision about self-reporting of elder mistreatment. The **VOICES** tool is currently being evaluated with older adults *in emergency department settings*. **More than** 800 older adults have used the VOICES tool so far without any issues. Study participants have demonstrated signs of feasibility, acceptance, demand, and full completion of the tool for those who consented to participate. There is an opportunity to expand the use of the **VOICES** tool to a more vulnerable older adult populations, such as older adults in primary care settings.

2.2 Background/Prevalence of Research Topic

Elder mistreatment (EM) is a major public health problem with estimated prevalence in the United States ranging from 27.9% to 62.3% for emotional abuse and 3.5%–23.1% for physical abuse among older adults with cognitive impairment (CI). EM consists of physical, emotional, sexual and financial abuse as well as neglect committed by a person in a position of trust to the older adult. It causes serious adverse outcomes for its victims including injury, increased service utilization, mental distress and the risk of mortality. A major barrier in overcoming EM is the inability to accurately identify EM victims. It is estimated that only 1 in 24 cases become known to authorities.

There are several perceived barriers to self-disclosure (informing others about the EM experiences) that limit help-seeking behaviors, including fear of nursing home placement, of losing autonomy or a caregiver, and of getting an abusive family member in legal trouble. As a result, reporting of EM remains low and providers often miss the opportunity to identify EM at point-of-care.

In our parent project, we used Digital Health frameworks to develop the Virtual cOaching in making Informed Choices on Elder Mistreatment Self-Disclosure (VOICES) tool. This is a new and innovative digital health tool that screens, educates, and motivates older adults to make an informed decision about self-identification (recognizing that they themselves are victims) and self-disclosure of elder mistreatment.

3 Rationale/Significance

3.1 Problem Statement

Is the VOICES tool (IRB Protocol ID:2000023799 and Submission ID:CR00008317), currently developed for older adults and evaluated in emergency department settings, feasible for use for older adults in primary care settings?

3.2 Purpose of Study/Potential Impact

Our aim is to perform a feasibility evaluation (N=80) of the VOICES screening tool among older adults in the primary care setting. If VOICES is feasible for identifying suspicion of EM in primary care setting, then we will be able to connect more victims of EM to necessary services and potentially prevent a multitude of poor EM outcomes.

3.2.1 Potential Risks

There are no medical interventions in this study, and direct medical risks are minimal. However, identification of potential EM without adequate safeguards could increase the risk of physical harm, emotional harm, risk of neglect, and financial loss to the victim. In addition, EM identification can potentially lead to adverse events including:

- retaliation of a family member or caregiver,
- an older adult may lose the caregiver or be abandoned by a caregiver, and a family member or paid caregiver may be arrested / incarcerated,
- discharge of a patient to a long-term care or skilled nursing facility, which they may not be able to afford,
- distress/anxiety during and/or after using the VOICES tool is a potential risk given the complex emotions typically associated with this phenomenon.
- there is a risk of compromised security of personal information.

Many of these adverse events would likely occur as a result of the mandatory report to Connecticut Protective Services for the Elderly (PSE) that the care team (case manager, clinician, nurses, and attendings) would make. However, during this study the care team is NOT expected to discover information that will require them to make a report to PSE.

Minimizing Risks:

Risks will be minimized through appropriate participant exclusions and close medical supervision throughout the protocol. We will inform all participants that there is a chance that they may experience adverse events due to the identification of EM by participating in the study and that their participation is voluntary. We will also remind participants that they can discontinue participation at any time.

In Summary: VOICES' goal is to help identify cases of EM. The subsequent procedures for the EM identification are important but are similar to the case when a provider identify suspicion of EM during normal clinical care:

- all patients who screen positive with the VOICES tool will be reviewed and assessed by YIMA care team.
- while the research team recognizes that the EM identified through the VOICES tool may lead to risks for patients that are usually associated with EM identification, we anticipate that the care team response will minimize the possible adverse events due to the EM identification.
- We will train all RAs to detect common signs of distress and anxiety. If any are even suspected of being observed, the care team at YIMA, will be contacted immediately for consultation and next steps, which could include counseling, referrals, or a psychiatric evaluation.
- If the older adult screens positive on the VOICES for EM or the older adult wants to self-disclose EM, the RA will notify the care team in the YIMA that there is suspicion of EM. Also, if the tool fails to identify EM but the patient would like to disclose EM, the RA will notify the care team. The RA will stay with the participant until a member of the care team arrives and implements existing protocols for handling EM identification.

- The care team can address each patient's concerns around reporting, immediate safety concerns, and any concerns for retaliation or abandonment. If the assessment indicates suspicion of abuse, and the case gets reported to PSE, usually PSE will arrive within 12 hours to take care of the case. While waiting for PSE, the health care team members will discuss safety issues with the patient.
- We will protect against psychological distress by informing all participants that there is a chance that they may experience some negative emotions while completing the surveys, after completing survey, or when they leave the hospital, but that they do not have to answer questions that they find distressing. We will also remind participants that they can discontinue participation at any time. We will also provide all older adults that we approach with the brochure on resources for aging well that also include free referral line. These options will be discussed with participants during initial recruitment.
- Although privacy and confidentiality will be preserved to the utmost extent possible, participants will be informed that, should EM be identified, the RA will report this to the care team in the YIMA. For example, if in the course of research procedures, a participant reveals elder abuse to the RA, the RA will discuss with the participant his/her responsibility to report the abuse to the care team. The physician will be notified of any suspicion of abuse and will determine through an evaluation whether the patient is in immediate danger or requires a report to PSE. If the care team performs the EM assessment and finds a suspicion of abuse, they will intervene to ensure patient safety. Also, if the participant divulges suicidality, the RA must report this to the care team and notify the PI.
- We will follow standard hospital operating procedures to guard against the possibility of study coercion, loss of confidentiality, psychological distress, and escalation of abuse, acknowledging that awareness or suspicion of reporting may anger the abuser but can also empower the patients and ultimately, make them safer.
- Our intent is to conduct a VOICES study session **without the presence** of the caregiver/LAR. From our experience, family members usually volunteer to leave the room.
- We will ask the caregivers to leave the room before engaging the older adults in using the VOICES tool and after the consent and assent. If the older adult wants the caregiver to remain, we will respect their wishes, but that patient will be excluded from the study and no study information will be presented.
- If a participant reveals depression, the research assistant will notify the care team. If a participant reveals severe depression or suicidality, or requests immediate psychiatric care for any reason, the RA will alert the patient's clinician to initiate an immediate psychiatric evaluation.
- Since the VOICES tool is a web-based application in nature, **no information** will be stored on the tablet. If the tablet gets lost or stolen, the patient's data

will not be compromised. All iPads contain encryption software, per University Policy 5100.

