6.1.2 Device Administration and Schedule

The VOICES tool will be provided on an iPad to the eligible participant and self-administrated by the participant. The research assistant will provide technical assistance if necessary, but otherwise the participant is expected to go through the tool independently, guided by the tool's virtual coach.

We will assess the patient ability to consent by checking if the patient can:

- articulate a choice regarding study participation
- understand its purpose
- comprehend that participation does not constitute medical treatment

If the patient has the capacity to consent, then he/she will complete the consent process on their own.

If patient does not have the capacity to consent, the LAR will need to consent.

If the LAR is not present at the clinic, we will seek to obtain the consent remotely.

After the patient completes the consent process and (if needed) the LAR completes the consent process, the LAR will be asked to wait in the waiting room and away from the room where study is being conducted. The patient will undergo the study procedures on their own without the presence of the LAR. If the LAR did not leave the room, or if the patient wanted them to be present then the patient will not be eligible for the study and cannot participate.

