6.3.2 Informed Consent

We will pay special attention to the ethical issues and the unique challenges of EM research as well as to consenting and enrolling older persons in our study. The consent process informs a volunteer about the study and fully explains the purpose of the research, that this is a research study, that participation is voluntary, and that the participant has the right to stop at any time. Our consent includes all of the eight basic elements of informed consent as articulated by 45 CFR §46.116, 21 CFR §50 and Yale IRB Policy 200 Informed Consent for Human Research) and the additional elements of informed consent. Before agreeing to participate in VOICES, potential subjects (and if needed their LAR) will be made aware of and understand the risks of participation. They are the following:

- A statement that the study involves research. This includes:
 - An explanation of the purposes of the research, stressing that this is not an intervention
 - The expected duration of the subject's participation
 - A description of the procedures to be followed
 - A description of any foreseeable risks or discomforts to the subject.
 - A description of any expected benefits to the subject or to others
 - When applicable, a disclosure of appropriate alternative
 - A statement explaining how confidentiality of data will be managed
 - An explanation of the risk of injury
 - List of whom to contact with questions about the research, research subjects' rights, or in the event of a research-related injury to the subject, that include: Principal Investigator's contact information and IRB Administrator's contact information
- A statement that:
 - Participation is voluntary
 - Refusal to participate will involve no penalty or loss of benefits to which the subject is otherwise entitled
 - The subject may discontinue participation at any time without penalty or loss of benefits to which the subject is otherwise entitled.
- In addition to the eight required elements of informed consent, additional elements are added to the consent. They include:
 - A statement that VOICES may involve risks to the subject which are currently unforeseeable;

- Anticipated circumstances in which the subject's participation may be terminated by the PI;
- Any additional costs to the subject that may result from participation in the research;
- The consequences of a subject's decision to withdraw from the research and procedures for orderly termination of participation by the subject;

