6.3.5 On Study Visits

There will be only one study visit necessary, which will be approximately a 45–60-minute session including:

- Introduction of study by research assistant
- Consent/Accent
- VOICES Tool self-administered by the eligible subject
- Post-use survey
- Incentive and resources to be given at end of study
- If the patient is eligible and would like to participate in the study, the RA will conduct the consent process (and if needed a consent from the LAR and assent from the subject) in a private exam room dedicated for this study. Participants (and if needed their LAR) must be able to consent and communicate in English. For all patients participating in this study, the consent will be requested from the patient and if needed from the LAR. Participants must be able and agree to use a tablet computer.
- If the LAR is needed for consent, and present in the clinic, verbal consent will be obtained.
- If the LAR is needed for consent and is not present in the clinic, verbal consent will be obtained via telephone.
- Important considerations
 - At the end of the consent process, the RA will review the subject's understanding of the study by asking the following question:
 - What are you being asked to do?
 - What questions is this study trying to answer?
 - What are the potential risks and benefits of participating in this study?
 - Can you withdraw from the study, and what should you do if you decide to withdraw?
 - Do you understand that participation in this study is voluntary and is not part of your medical treatment?
 - The caregiver (if any is present) will be asked to step out of the room and go wait in the family room. The patient will undergo the study producers on their own without the presence of the caregiver. If the caregiver did not leave the room, or if the patient wanted them to be present then the patient will not be eligible for the study and cannot participate.
 - Participants will be given a description of the study and that they are testing the feasibility of VOICES and that the evaluation is not a measure of their individual performance but measure of the tool performance.
 - The RA will collect the participant demographics to gather background information on the participants.

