4.1 Primary Outcome

Implementation in Terms of Participation. Participation will be determined by the ratio of participants who are successfully enrolled to the total number of eligible patients.

Implementation in Terms of Usage. Usage will be determined by the number of consented participants enrolled in the study who used VOICES to completion.

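### Caregivers are asked to leave only after consent, so the promise to present no study information if they stay cannot hold, and calling those patients ineligible may shrink the Participation denominator

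*Protocol*

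**What the plan says.** Protocol 3.2.1 (Minimizing Risks) says caregivers will be asked to leave "before engaging the older adults in using the VOICES tool and after the consent and assent". The next sentence covers the older adult who wants the caregiver to remain: "that patient will be excluded from the study and no study information will be presented".

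Two other sections describe the same step. Protocol 6.1.2 deals with the legally authorized representative (LAR): once consent is complete, "the LAR will be asked to wait in the waiting room and away from the room where study is being conducted". Protocol 6.3.5 deals with caregivers, in a list of considerations and after the comprehension questions that close consent: "The caregiver (if any is present) will be asked to step out of the room and go wait in the family room". Both sections say that the patient is not eligible if the person stays or the patient wants them to stay.

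Protocol 6.3.2 says that consent "fully explains the purpose of the research" and makes the patient, and the LAR if one is needed, aware of the risks. Protocol 3.2.1 lists "retaliation of a family member or caregiver" among the possible adverse events, and acknowledges that an abuser who knows of or suspects a report may be angered.

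SAP 4.1 defines Participation, a primary outcome, as the "ratio of participants who are successfully enrolled to the total number of eligible patients".

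**The concern.** The sentence in 3.2.1 reads as a safeguard: if the caregiver will not leave, nothing about the study is disclosed. In the order that the same section gives, it cannot work. The decision to stay or leave comes after the conversation that discloses the purpose and risks. In a study of elder mistreatment, the person in the room may be the person concerned, and the protocol treats that person's reaction as a source of harm.

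There is also a counting problem. A patient who has consented and meets every listed criterion can become ineligible because a caregiver stays. Whether older adults in this clinic can be seen alone bears directly on implementation. If these patients leave the denominator through an eligibility label, the study loses that information and Participation looks better than it was.

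**Working it through.** The plan states no figure on this point, so the check is mainly a comparison of sections.

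**1. Order of steps.** Protocol 3.2.1 explicitly places the caregiver's exit after consent and assent and before the tool is used. Section 6.1.2 explicitly places the LAR's exit after consent. In 6.3.5 the caregiver item has no timing of its own; its place after the comprehension questions agrees with 3.2.1 but does not prove the order.

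**2. What has been disclosed by then.** Under 6.3.2, the purpose, procedures, foreseeable risks and expected benefits. The questions at the end of consent (6.3.2 and 6.3.5) have the patient say aloud what the study is trying to answer and what its risks and benefits are.

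**3. Who could have heard it.** A consenting LAR must have been told. Any other caregiver could have heard it if present. No section requires that caregiver to be out of the room before the purpose is explained.

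**4. Status afterwards.** Sections 6.1.2 and 6.3.5 call the patient ineligible. None of the four exclusions in 5.3.2 concerns caregiver presence. Section 6.3.4 enrols only patients who have consented and meet all the criteria, so these patients are not enrolled.

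**5. Participation.** Let E be the number who meet the 5.3.2 criteria and k the number among them lost because a caregiver stays. Enrolled = 80 (SAP section 3). The documents give neither E nor k, so both are assumed.

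- These patients kept as eligible: 80/E.
- These patients dropped as ineligible: 80/(E − k).

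| Assumed E | Assumed k | Kept | Dropped | Difference |
|---|---|---|---|---|
| 160 | 10 | 80/160 = 50.0% | 80/150 = 53.3% | 3.3 points |
| 160 | 20 | 80/160 = 50.0% | 80/140 = 57.1% | 7.1 points |
| 164 | 4 | 80/164 = 48.8% | 80/160 = 50.0% | 1.2 points |
| 106 | 16 | 80/106 = 75.5% | 80/90 = 88.9% | 13.4 points |

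The last two rows are the extremes when E − k runs from 90 to 160 and k from 4 to 16. The direction is fixed, since 80/(E − k) exceeds 80/E whenever k > 0. The size depends wholly on the assumed counts.

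**6. Usage.** SAP 4.1 counts completers among consented participants enrolled in the study. By step 4 these patients are never enrolled, so they are outside the Usage base whether they are labelled ineligible or eligible but not enrolled. Usage does not change.

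**The case against.** The strongest reply is that exposure is not shown. Section 6.3.5 puts consent in a private exam room. Section 6.1.2 has patients with capacity go through consent by themselves. Section 3.2.1 reports that relatives usually offer to leave. Section 5.3 describes a population without cognitive impairment, so LAR consent should be uncommon, and an LAR who consents has to be told about the study anyway. This makes overhearing less likely, but none of it requires a caregiver to be absent during consent. The wording on patients with capacity contrasts them with LAR consent; it does not say who may be in the room.

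The disputed sentence might also mean only tool content or further information, since 6.3.5 lists a description of the study after the caregiver item. That reading is possible, but the text does not state it, and it would still leave the purpose and risks disclosed.

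On counting, the SAP does not say that these patients are dropped. A denominator built from the list in 5.3.2 could already include them. Conversely, a patient who declines a private session arguably fails the inclusion criterion on willingness to comply with all procedures. Both points stand. They show that the denominator is open to more than one reading.

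A reader might infer more than the documents support:

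- That an abuser does hear the study's purpose. This is possible, not stated.
- That consent tells a caregiver about reporting to the care team. The consent elements in 6.3.2 do not name it; 3.2.1 says participants are told, without saying when.
- That Usage is inflated as well. It is not, by step 6 of the working.

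**Conclusion.** The contradiction in Protocol 3.2.1 is real. With the caregiver's exit placed after consent, the promise to withhold study information comes too late. That a caregiver overhears is a possibility left open by the order of steps, and its frequency cannot be derived from the documents.

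The label in 6.1.2 and 6.3.5, read literally, removes these patients from the Participation denominator although 5.3.2 contains no such exclusion. The ratio could then only rise. The amount is unknown: the illustrations run from 1.2 to 13.4 percentage points and rest on assumed counts, so they should not be quoted as an estimate of bias.

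The point should be acted on, because it concerns a harm that the protocol names and the definition of a primary outcome, and the remedy is cheap.

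**What to change.** - Reconcile Protocol 3.2.1, 5.3.2, 6.1.2 and 6.3.5 on when the caregiver or LAR leaves and what follows if they stay.
- For patients with capacity, place the request for the caregiver to leave before the consent discussion.
- State separately what an LAR who must consent is told.
- Correct the sentence in 3.2.1 so that it promises only what the order of steps can deliver.
- In SAP 4.1 and 7.1, count patients who meet the 5.3.2 criteria but want the caregiver to stay as eligible, not enrolled, and report their number. Say that this wish alone does not fail the willingness criterion.

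The SAP (Study Summary, revised 5/16/2023, and section 3) reports that the 80 participants have been recruited, so reordering cannot change their sessions. It applies to any further use of the script, including the future pilot that Protocol 5.1 says this study will guide. The counting rule applies to this study's report, as far as the screening and enrolment records identify these patients; if they do not, the report should say so. The cost is a wording amendment, one reordered step and one reporting line, with no extra staff or visits.
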